## **6.2. Secondary Endpoint(s)**

### **6.2.1. Safety endpoints**

Refer to Section 6.6.

## **6.2.2. Efficacy endpoints**

### **Combinations A and F**

The following analyses will be based on the FAS by treatment group using the data from the combined Phases 1b and 2 (Cohorts A1, A2, A3 and Cohorts F1, F2 and F3) and the data from Phase 2 (Cohorts A4, A5, A6, A7, A8, A9, A10).

### **Combinations B, C and D**

The following analyses will be based on the FAS by treatment group using the data from Phase 1b and from Phase 2 separately and for each combination.

Tumor-related endpoints will be analyzed based on investigator assessment using RECIST v1.1. In addition to what is described below, the objective response (OR) will also be analyzed similar to that described in Section 6.1.2.1 for each of the Phase 1b cohorts of Combinations B, C and D.

#### **6.2.2.1. Tumor shrinkage from baseline**

Tumor shrinkage will be summarized as the percent change from baseline in target lesions (sum of longest diameter for non-nodal lesion and short axis for nodal lesion) per time point. It will be derived as:

- $((\text{Sum of target lesions at week XX} - \text{sum of target lesions at baseline}) / \text{sum of target lesions at baseline}) \times 100$

The maximum reduction in target lesions from baseline will be derived across all the post-baseline assessments until documented disease progression, excluding assessments after start of subsequent anti-cancer therapy, as:

- $\text{Minimum of } ((\text{sum of target lesions at week XX} - \text{sum of target lesions at baseline}) / \text{sum of target lesions at baseline}) \times 100$

A waterfall plot of maximum percent reduction in the sum of longest diameter for non-nodal lesions and short axis for nodal lesions from baseline will be created by treatment group. These plots will display the best percentage change from baseline in the sum of the diameters of all target lesions for each patient with measurable disease at baseline and at least one post-baseline assessment.

#### **6.2.2.2. Disease control**

Disease Control (DC) is defined as BOR of CR, PR, non-CR/non-PD or SD. DC rate (DCR) is the proportion of patients with DC.

DCR will be summarized by frequency counts and percentages.

#### **6.2.2.3. Duration of response**

Duration of Response (DR) is defined, for patients with OR, as the time from the first documentation of objective response (CR or PR) to the date of first documentation of PD or

death due to any cause. If a patient has not had an event (PD or death), DR is censored at the date of last adequate tumor assessment. The censoring rules for DR are described in Table 9.

$$\text{DR (months)} = [\text{date of event or censoring} - \text{first date of OR} + 1] / 30.4375$$

**Table 9. Outcome and Event Dates for DR Analyses**

Scenario	Date of event/censoring	Outcome
PD or death - After at most one missing or inadequate post-baseline tumor assessment, OR - ≤ 16 weeks after the ‘start date’	Date of PD or death	Event
PD or death - After 2 or more missing or inadequate post-baseline tumor assessments	Date of last adequate tumor assessment a documenting no PD before new anti-cancer therapy is given or missed tumor assessments	Censored
No PD and no death	Date of last adequate tumor assessment a documenting no PD before new anti-cancer therapy is given or missed tumor assessments	Censored
Treatment discontinuation due to ‘Disease progression’ without documented progression	Not applicable	Information is ignored. Outcome is derived based on documented progression only.
New anti-cancer therapy given	Date of last adequate tumor assessment a documenting no PD before new anti-cancer therapy is given or missed tumor assessments	Censored

a If there are no adequate post-baseline assessments prior to PD or death, then the time without adequate assessment should be measured from the ‘start date’; if the criteria were met the censoring will be on the ‘start date’.

Kaplan-Meier estimates (product-limit estimates) will be presented by treatment group together with a summary of associated statistics including the median DR time with 2-sided 95% CIs. In particular, the DR rates at 2, 4, 6, 8, 10 and 12 months will be estimated with corresponding 2-sided 95% CIs. The CIs for the median will be calculated according to Brookmeyer and Crowley (1982) and the CIs for the survival function estimates at the time points defined above will be derived using the log-log transformation according to Kalbfleisch and Prentice (2002) (conftype=loglog default option in SAS Proc LIFETEST) with back transformation to a CI on the untransformed scale. The estimate of the standard error will be computed using Greenwood’s formula.

DR will be displayed graphically and analyzed using Kaplan-Meier methodology. If the number of patients with OR is small, the Kaplan-Meier method may not provide reliable estimates. In this case, only descriptive statistics or listings will be provided.

Frequency (number and percentage) of patients with each event type (PD or death) and censoring reasons will be presented by treatment group. Reasons for censoring will be summarized according to the categories in Table 10 following the hierarchy shown.

**Table 10. DR Censoring Reasons and Hierarchy**

Hierarchy	Condition	Censoring Reason
1	Start of new anti-cancer therapy	Start of new anti-cancer therapy
2	Event after 2 or more missing or inadequate post-baseline tumor assessments/date of randomization	Event after 2 or more missing assessments a
3	No event and [withdrawal of consent date ≥ date of randomization OR End of study (EOS) = Patient refused further follow-up]	Withdrawal of consent
4	No event and lost to follow-up in any disposition page	Lost to follow-up
5	No event and [EOS present OR disposition page for any epoch after screening says patient will not continue into any subsequent phase of the study] and no adequate post-baseline tumor assessment	No adequate post-baseline tumor assessment
6	No event and none of the conditions in the prior hierarchy are met	Ongoing without an event

a 2 or more missing or inadequate post-baseline tumor assessments.

#### 6.2.2.4. Time to response

Time to response (TTR) is defined, for patients with OR, as the time from the ‘start date’ to the first documentation of objective response (CR or PR) which is subsequently confirmed.

$$\text{TTR (in months)} = [\text{first date of OR} - \text{‘start date’} + 1] / 30.4375$$

TTR will be summarized using simple descriptive statistics (mean, SD, median, min, max, Q1, Q3).

#### 6.2.2.5. Progression-free survival

Progression-Free Survival (PFS) is defined as the time from the ‘start date’ to the date of the first documentation of PD or death due to any cause, whichever occurs first.

PFS data will be censored on the date of the last adequate tumor assessment for patients who do not have an event (PD or death), for patients who start a new anti-cancer therapy prior to an event (see Section 5.2.6) or for patients with an event after 2 or more missing tumor assessments. Patients who do not have an adequate baseline tumor assessment or who do not have an adequate post-baseline tumor assessment will be censored on the ‘start date’ unless death occurred on or before the time of the second planned tumor assessment (ie ≤ 16 weeks after the ‘start date’) in which case the death will be considered an event.

In this study antitumor activity will be assessed through radiological tumor assessments conducted at screening and every 8 weeks (±7 days) until PD regardless of initiation of subsequent anti-cancer therapy. After 1 year from the ‘start date’, tumor assessments will be

conducted at 12-week ( $\pm 7$  days) intervals and after 2 years from the ‘start date’, tumor assessments will be conducted at 16-week ( $\pm 7$  days) intervals.

The censoring and event date options to be considered for the PFS and DR analysis are presented in Table 11.

$$\text{PFS (months)} = [\text{date of event or censoring} - \text{‘start date’} + 1] / 30.4375$$

**Table 11. Outcome and Event Dates for PFS Analyses**

Scenario	Date of event/censoring	Outcome
No adequate baseline assessment	‘Start date’ a	Censored a
PD or death - After at most one missing or inadequate post-baseline tumor assessment, OR - $\leq 16$ weeks after the ‘start date’	Date of PD or death	Event
PD or death - After 2 or more missing or inadequate post-baseline tumor assessments	Date of last adequate tumor assessment b documenting no PD before new anti-cancer therapy is given or missed tumor assessments	Censored
No PD and no death	Date of last adequate tumor assessment b documenting no PD before new anti-cancer therapy is given or missed tumor assessments	Censored
Treatment discontinuation due to ‘Disease progression’ without documented progression	Not applicable	Information is ignored. Outcome is derived based on documented progression only.
New anti-cancer therapy given	Date of last adequate tumor assessment b documenting no PD before new anti-cancer therapy is given or missed tumor assessments	Censored

a However if the patient dies  $\leq 16$  weeks after the ‘start date’ the death is an event with date on death date

b If there are no adequate post-baseline assessments prior to PD or death, then the time without adequate assessment should be measured from the ‘start date’; if the criteria were met the censoring will be on the ‘start date’

Kaplan-Meier estimates (product-limit estimates) will be presented by treatment group together with a summary of associated statistics including the median PFS time with 2-sided 95% CIs. In particular, the PFS rate at 2, 4, 6, 8, 10, 12 and 18 months will be estimated with corresponding 2-sided 95% CIs. The CIs for the median will be calculated according to Brookmeyer and Crowley (1982) and the CIs for the survival function estimates at the time points defined above will be derived using the log-log transformation according to Kalbfleisch and Prentice (2002) (conftype=loglog default option in SAS Proc LIFETEST) with back transformation to a CI on the untransformed scale. The estimate of the standard error will be computed using Greenwood’s formula.

Frequency (number and percentage) of patients with each event type (PD or death) and censoring reasons will be presented by treatment group. Reasons for censoring will be summarized according to the categories in Table 12 following the hierarchy shown.

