### **5.2.11. Adequate post-baseline tumor assessment**

An adequate post-baseline assessment is defined as an assessment where a response of CR, PR, SD, non-CR/non-PD, or PD can be determined (see Section 6.1.2.1). Time points where the response is not evaluable (NE) or no assessment was performed will not be used for determining the censoring date.

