**Table 12. PFS Censoring Reasons and Hierarchy**

Hierarchy	Condition	Censoring Reason
1	No adequate baseline assessment	No adequate baseline assessment
2	Start of new anti-cancer therapy	Start of new anti-cancer therapy
3	Event after 2 or more missing or inadequate post-baseline tumor assessments/'start date'	Event after missing assessments a
4	No event and [withdrawal of consent date ≥ 'start date' OR End of study (EOS) = Patient refused further follow-up]	Withdrawal of consent
5	No event and lost to follow-up in any disposition page	Lost to follow-up
6	No event and [EOS present OR disposition page for any epoch after screening says patient will not continue into any subsequent phase of the study] and no adequate post-baseline tumor assessment	No adequate post-baseline tumor assessment
7	No event and none of the conditions in the prior hierarchy are met	Ongoing without an event

a 2 or more missing or inadequate post-baseline tumor assessments.

The PFS time or censoring time and the reasons for censoring will also be presented in a patient listing.

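### Tables 11 and 9 add an uncounted missed-scan condition to the event-free and new-therapy rows, against the text of 6.2.2.5 and 6.2.2.3; read literally, it makes PFS and DR censoring depend on outcome

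*SAP*

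**What the plan says.** **Text.** SAP 6.2.2.5 states: "PFS data will be censored on the date of the last adequate tumor assessment for patients who" have no event. The same sentence covers patients who start a new therapy before an event, and adds a missed-scan condition only for those who do have an event: "or for patients with an event after 2 or more missing tumor assessments". SAP 6.2.2.3 likewise censors DR at the last adequate tumor assessment when there is no PD or death.

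**Tables.** In Table 11, three rows share one censoring date: the last adequate assessment "documenting no PD before new anti-cancer therapy is given or missed tumor assessments". They are the row for PD or death after two or more missing assessments, the row for no PD and no death, and the row for new anti-cancer therapy. Only the first gives a count. Table 9 repeats the wording for DR. In both tables PD or death is an event on its own date when it comes "After at most one missing or inadequate post-baseline tumor assessment".

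**Related rules.** Table 12 has a missed-assessment censoring reason only for patients with an event, and its footnote defines the gap as "2 or more missing or inadequate post-baseline tumor assessments". Table 10 does the same for DR. SAP 5.2.11 adds: "Time points where the response is not evaluable (NE) or no assessment was performed will not be used for determining the censoring date". Scans are planned "every 8 weeks (±7 days) until PD regardless of initiation of subsequent anti-cancer therapy", every 12 weeks after year 1 and every 16 weeks after year 2.

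**The concern.** In the row for events after two or more missing assessments, the shared phrase has a clear job: it moves the date back to before the gap. In the other two rows it has no such job and no count. A programmer who treats it alike everywhere will cut an event-free patient back to the scan before the first missed one and discard every later scan without PD.

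Post-gap follow-up would then count only when it ends in PD or death. Keeping or dropping time at risk according to the outcome is informative censoring. It removes patients from the Kaplan-Meier risk set because they stayed progression-free, and it pulls the curve down relative to the text rule.

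The censoring summary would not reveal this. A patient cut back in this way who meets no earlier condition in Table 12 falls into the last category, ongoing without an event. Section 6.2.2.5 also sends the reader to Table 11 for the event and censoring dates, so the table may well be what is coded.

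**Working it through.** **No plan figure to reproduce.** The SAP gives no expected PFS or DR rate, event count or missed-scan rate. The one related number, 16 weeks for the second planned scan, follows from 2 × 8 = 16.

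**Step 1: one patient under each rule.** Adequate scans without PD at weeks 8 and 16, week 24 missed, adequate scans without PD at weeks 32, 40 and 48, no new therapy. PFS in months = (date − start date + 1) / 30.4375.

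- Text of 6.2.2.5: censored at week 48, (336 + 1) / 30.4375 = 11.1 months.
- Table 11, any missed scan: censored at week 16, (112 + 1) / 30.4375 = 3.7 months.
- Table 11, two or more consecutive missed scans: no such gap, so week 48, as in the text.
- Same gap but PD at week 48: one missing assessment, so an event at 11.1 months.

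On the any-scan reading, the 7.4 months after week 16 count if the patient progresses and are lost if the patient does not.

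**Step 2: size for PFS.** Simulation of 40,000 patients per scenario on the SAP scan schedule. Assumptions not in the SAP: exponential PFS with median 2, 4 or 8 months; 15% of events are deaths; each scan missed independently with probability 5%, 10% or 20%; follow-up uniform over 12–24 or 18–36 months. Kaplan-Meier PFS rate at 18 months (%):

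| Median, follow-up (months) | Missed | All scans done | Text rule | Table: 2+ consecutive | Table: any scan | Text − 2+ | Text − any |
|---|---|---|---|---|---|---|---|
| 8, 12–24 | 5% | 23.1 | 23.2 | 23.0 | 18.5 | 0.2 | 4.7 |
| 8, 12–24 | 10% | 22.7 | 23.2 | 22.3 | 14.7 | 0.9 | 8.5 |
| 8, 12–24 | 20% | 23.1 | 25.1 | 22.0 | 10.0 | 3.1 | 15.1 |
| 8, 18–36 | 5% | 23.2 | 23.6 | 23.5 | 21.1 | 0.1 | 2.5 |
| 8, 18–36 | 10% | 23.5 | 24.4 | 23.9 | 19.8 | 0.5 | 4.6 |
| 8, 18–36 | 20% | 23.5 | 26.1 | 24.1 | 17.7 | 2.0 | 8.4 |
| 4, 12–24 | 10% | 5.3 | 5.5 | 5.3 | 3.3 | 0.2 | 2.2 |
| 4, 18–36 | 10% | 5.4 | 5.8 | 5.7 | 4.9 | 0.1 | 0.9 |

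With a median of 2 months the any-scan reading differs from the text by at most 0.2 points at 18 months, because few patients are still event-free. At 12 months the any-scan difference runs from 0 to 40.7 − 29.4 = 11.3 points.

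**Step 3: a mixture with long-term responders.** Assumed: 25% of patients with median 24 months, or 40% with median 30 months, the rest progressing early; follow-up 18–36 months; every event found at a scan. PFS rate at 18 months (%):

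| Long-term share | Missed | All scans done | Text | 2+ consecutive | Any scan |
|---|---|---|---|---|---|
| 25% | 5% | 15.5 | 15.7 | 15.6 | 13.2 |
| 25% | 10% | 15.5 | 16.1 | 15.6 | 11.2 |
| 40% | 10% | 27.3 | 28.1 | 27.4 | 21.0 |

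The any-scan reading loses 2.5, 4.9 and 7.1 points against the text. The two-or-more reading loses 0.1, 0.5 and 0.7.

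**Step 4: consecutive or cumulative.** The event rows do not say that the missing assessments must be consecutive. For nine scans missed independently with probability p, P(at least 2 missed) = 1 − (1 − p)^9 − 9p(1 − p)^8. That is 7.1% at p = 0.05 and 22.5% at p = 0.10. The probability that the last two are both missed is p², or 0.25% and 1%.

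**The case against.** The strongest reply is that the any-scan rule is not what the SAP says but one reading of a repeated, uncounted phrase. The first row carrying the phrase is headed two or more missing, and the Table 12 footnote uses the same count. Both narrative sections censor event-free patients at the last adequate assessment. Section 5.2.11 leans the same way, and neither Table 10 nor Table 12 has a category for an event-free patient cut back at a gap. This stands: a reader might infer that the SAP has fixed a rule to censor before any missed scan, and the documents do not support that.

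A reader might also infer that late PFS rates are biased downward without qualification. That too goes beyond the evidence. The downward shift is relative to the text rule, which itself drifts up as scans are missed because PD is then dated late. Against complete scanning the net effect can reverse: with median 4 months, follow-up 18–36 months and 20% missed, the any-scan reading gives a 12-month rate of 15.2% against 14.4% with all scans done.

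On consecutive gaps, the footnotes to Tables 11 and 9 speak of the time without adequate assessment, which describes one continuous interval before the event. Voiding a well-documented PD because of two isolated misses is therefore a strained reading, though the rows themselves do not exclude it.

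Finally, formal tests concern ORR only. With 28 patients and a rate near 16%, a simple 95% half-width is 1.96 × √(0.16 × 0.84 / 28) = 0.136, about 14 points. PFS times and censoring reasons are also listed by patient. These points limit the consequence but do not remove the contradiction: imprecision does not offset a systematic shift, and the listed reason would not show that a gap had moved the date.

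**Conclusion.** The contradiction is established from the wording alone. The event-free and new-therapy rows of Tables 11 and 9 carry a condition that the text does not apply to those patients, that has no count, and that has no matching censoring reason in Tables 12 and 10.

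The effect on results is conditional. On the any-scan reading the 18-month PFS rate is 0 to about 15 points below the text rule. It is near zero where almost everyone progresses early, and material where PFS is long, follow-up short or missed scans common. On the reading of two or more consecutive missed scans the loss is at most 0.2 points with 5% missed, about 1 point with 10% and about 3 points with 20%. These sizes rest on assumed medians, follow-up and independent missed scans, none of which the SAP supplies. For DR the mechanism is the same, but no size was computed, and the SAP allows descriptive statistics or listings instead of Kaplan-Meier when responders are few.

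PFS and DR are secondary and descriptive. No hypothesis test, decision rule or sample size is affected.

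**What to change.** - In Tables 11 and 9, in the rows for no PD and no death and for new anti-cancer therapy, delete the closing clause on missed assessments. The date is then the last adequate assessment documenting no PD before any new anti-cancer therapy, in line with 6.2.2.5 and 6.2.2.3.
- Keep that clause in the row for events after a long gap, where it is needed. Define the gap there as *2 or more consecutive missing or inadequate assessments immediately before the PD or death*, and word the row for at most one missing assessment as its complement. This agrees with the footnotes on time without adequate assessment.
- Carry the same definition into the event-after-missing-assessments lines of Tables 10 and 12, and into the sentence in 6.2.2.5.

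The cost is SAP wording and a matching check of the derivation program. No new data are needed.

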**Table 12. PFS Censoring Reasons and Hierarchy**

Hierarchy	Condition	Censoring Reason
1	No adequate baseline assessment	No adequate baseline assessment
2	Start of new anti-cancer therapy	Start of new anti-cancer therapy
3	Event after 2 or more missing or inadequate post-baseline tumor assessments/'start date'	Event after missing assessments a
4	No event and [withdrawal of consent date ≥ 'start date' OR End of study (EOS) = Patient refused further follow-up]	Withdrawal of consent
5	No event and lost to follow-up in any disposition page	Lost to follow-up
6	No event and [EOS present OR disposition page for any epoch after screening says patient will not continue into any subsequent phase of the study] and no adequate post-baseline tumor assessment	No adequate post-baseline tumor assessment
7	No event and none of the conditions in the prior hierarchy are met	Ongoing without an event

a 2 or more missing or inadequate post-baseline tumor assessments.

The PFS time or censoring time and the reasons for censoring will also be presented in a patient listing.

#### 6.2.2.6. Overall Survival

Overall survival (OS) is defined as the time from the 'start date' to the date of death due to any cause. Patients last known to be alive will be censored at date of last contact.

$$\text{OS (months)} = [\text{date of death or censoring} - \text{'start date'} + 1] / 30.4375$$

Kaplan-Meier estimates (product-limit estimates) will be presented by treatment group together with a summary of associated statistics including the median OS time with 2-sided 95% CIs. In particular, the OS rate at 2, 4, 6, 8, 10, 12, 18 and 24 months will be estimated with corresponding 2-sided 95% CIs. The CIs for the median will be calculated according to Brookmeyer and Crowley (1982) and the CIs for the survival function estimates at the time points defined above will be derived using the log-log transformation according to Kalbfleisch and Prentice (2002) (conftype=loglog default option in SAS Proc LIFETEST) with back transformation to a CI on the untransformed scale. The estimate of the standard error will be computed using Greenwood's formula.

Frequency (number and percentage) of patients with an event (death) and censoring reasons will be presented by treatment group. Reasons for censoring will be summarized according to the categories in Table 13 following the hierarchy shown.

**Table 13. OS Censoring Reasons and Hierarchy**

Hierarchy	Condition	Censoring Reason
1	No event and [withdrawal of consent date $\geq$ 'start date' OR End of study (EOS) = Patient refused further follow-up]	Withdrawal of consent
2	No event and [lost to follow-up in any disposition page OR data cut-off date – last contact date > 16 weeks]	Lost to follow-up
3	No event and none of the conditions in the prior hierarchy are met	Alive

The OS time or censoring time and the reasons for censoring will also be presented in a patient listing.

OS analysis will be conducted for patients up to LSLV of the study.

